10.0 Local Number of Participants

10.1 Local Number of Participants to be Consented: 130

10.2 Basis for Sample Size Calculation:

The sample size of 98 total patients was calculated in consultation with a statistician on the assumption that there would be a significant mean difference of 0.5°C (SD=0.75) (see Section 15.2 for more details). To account for an 80% enrollment rate, we estimate we will need to approach 123 patients for the study.

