15.0 Statistical Considerations

15.1 Data Analysis Plan:

1. Our primary outcome variable is the patient's temperature at the end of surgery.

2. Secondary outcome variables also include:

- AUC of time versus temperature curves;
- temperatures at set points during operative period;
- blood loss volumes

All continuous measures will be summarized with mean (standard deviation) or median (interquartile range) based upon evaluation of normality using statistical tests (e.g., Shapiro-Wilk) and graphical representation (e.g., histograms, boxplots). Categorical measures will be summarized by count (percent).

The secondary outcomes are continuous measures and will be compared using two-sided two-sample t-tests for unadjusted comparisons of the groups. Adjusted comparisons will use linear regression models to account for potential confounders that may affect the outcome based upon the clinical literature.

Safety outcomes of interest include the incidence of hyperthermia, rescue warming, and incidence of thermal injury. These are categorical variables and will be compared using the χ^2 test or Fischer's exact test for unadjusted comparisons and with logistic regression models to account for potential confounders.

Final data set will be assessed for missing data, depending on rate of missing data, we will use statistical methods to account for missing data

15.2 Power Analysis:

A mean difference of 0.5°C in patient temperatures between the two devices would be clinically meaningful. However, limited data exists, so a range of standard deviations were explored to examine the different sample sizes needed at 80% and 90% power (assuming a two-sided two-sample t-test with $\alpha=0.05$).

Power	SD	N per Group	Overall N
0.8	0.25	6	12

MEDICAL PROTOCOL (HRP-590)

PROTOCOL TITLE: Comparison of normothermia maintenance between resistive blanket and forced air warming systems in renal transplant surgery

VERSION DATE: V43 January June 6, 2022

	0.5	17	34
	0.75	37	74
	1	64	128
0.9	0.25	7	14
	0.5	23	46
	0.75	49	98
	1	86	172

We will take a conservative approach by enrolling 49 patients per group (98 patients total). As this is a minimal risk study, we expect to an 80% enrollment rate; we will approach (98 + 20% = 123 patients). In 2019, the University of Minnesota Medical Canter performed approximately 240 renal transplants for a total of ~200 eligible patients or ~16 eligible patients/month; 100 total patients approached/16 eligible patients per month = 6.25 months.

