18.0 Provisions to Monitor the Data to Ensure the Safety of Participants

18.1 Data Integrity Monitoring:

A detailed review of all participants and participant data will be conduct at monthly intervals by the PI or co-PI to ensure data is being recorded and analyzed appropriately. Any missing data or abnormal data findings will trigger a detailed review of raw data from EPIC and measures will be taken to train the staff to minimize the chance for recurrence and to improve the process of data collection and analysis. The PI or co-PI will also review EPIC records of each subject to verify protocols were followed and to note if any adverse events occur, and if any rescue interventions were implemented and implemented correctly.

Any adverse events, whether related to the study or not with regards to temperature management, will be reported to the study team in addition to chart review. An adverse event log will be maintained, with events reported to the IRB. If there is any question as to whether the event was related to the study, the case will be referred to [name], the Department of Anesthesiology's Vice Chair for Research and the Departments Quality Assurance Event monitor, for review and adjudication. [name] will be empowered to temporarily halt enrollment if any safety concerns are noted - although the final decision regarding halting or resuming the study will be referred to the Department of Anesthesiology's DSMB (see below for details).

18.2 Data Safety Monitoring:

The Department of Anesthesiology has a designated "DSMB" headed by [name] and including Drs. [name] and [name]. Given the low risk

MEDICAL PROTOCOL (HRP-590)

PROTOCOL TITLE: Comparison of normothermia maintenance between resistive blanket and forced air warming systems in renal transplant surgery

VERSION DATE: V43 January June 6, 2022

nature of this study, our plan is for the DSMB to receive blinded (A vs B) data after the completion of the 55th patient (the halfway point). While statistical stopping rules for non-inferiority studies remain uncertain, we will use a well-established O'Brien-Fleming procedure and will stop the study if the SUPERIORITY of either method is established, based on an intergroup Z-score difference of 2.78.

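### The planned sample size is 98, but the 130 to be consented, the halfway look at patient 55 and the 100 approached do not match it

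*Combined protocol and SAP*

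**What the plan says.** - **Sample size.** Section 15.2 commits to "enrolling 49 patients per group (98 patients total"). Section 10.2 gives the same total, based on "a significant mean difference of 0.5°C (SD=0.75").
- **Approached.** Section 10.2 applies an 80% enrolment rate: "we estimate we will need to approach 123 patients for the study". Section 15.2 repeats 123, but labels the step as 98 plus 20%. Its accrual line then divides 100 approached by 16 eligible patients a month to get 6.25 months.
- **Consented.** Section 10.1 reads "Local Number of Participants to be Consented: 130". No derivation is given.
- **Interim look.** Section 18.2 sends data masked as A versus B to the DSMB "after the completion of the 55th patient (the halfway point"). The study stops if either method is shown superior, using an O'Brien-Fleming procedure with Z = 2.78.
- **Final test.** Section 15.3 sets significance at p < 0.05 and makes no allowance for the interim look.

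**The concern.** Section 10.1 plans more consents than section 10.2, directly below it, expects people to be approached. Patient 55 is half of neither 98 (half is 49) nor 130 (half is 65). Section 15.2 gives two different numbers approached in one paragraph.

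The interim mismatch matters most, because that look can end the trial. A group-sequential boundary belongs to a stated fraction of the information, and the final critical value follows from both. Here the label says 50%, the planned total says 56%, and no final value is given. The consent figure matters less. But clinicians in this trial know the allocation, so the protocol should say plainly when enrolment ends.

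**Working it through.** **Inputs.** Difference 0.5°C (15.2: "A mean difference of 0.5°C in patient temperatures between the two devices would be clinically meaningful"); SD 0.75 (10.2); two-sided two-sample t-test at α = 0.05 and 90% power (15.2); 1:1 allocation (5.1); 80% enrolment rate (10.2, 15.2); 16 eligible patients a month (15.2); look at patient 55 with Z = 2.78 (18.2); final p < 0.05, taken as 1.96 (15.3).

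**1. Sample size.** The normal approximation is n = 2(1.960 + 1.282)²(0.75/0.5)² = 47.3, so 48 per group. The exact t-test calculation gives 48.26, so 49 per group and 98 in total, with power 90.4%. The plan's figure reproduces.

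**2. Approached.** 98/0.80 = 122.5, so 123, and 123 × 0.80 = 98.4. The figures 98 and 123 agree. Taken literally, 98 plus 20% would be 117.6, so the label is wrong although the result is right.

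**3. Consented.** 130 is greater than 123. At 80%, 130 consents need 130/0.80 = 162.5, about 163 approached. If 130 allows for losses after consent, it implies that 98/130 = 75% of consented patients are randomised. No such rate is given.

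**4. Accrual.** 100/16 = 6.25 months, but 123/16 = 7.7 months. Both fit within the study duration of about one year in section 5.3.

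**5. Interim look.** The information fraction is t = 55/N. The two test statistics are bivariate normal with correlation √t, and overall error is 1 − P(|Z₁| < 2.78 and |Z₂| < 1.96). The classical O'Brien-Fleming bounds are C/√t at the look and C at the end, with C chosen so that overall error is 5%.

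| N | Half | 55/N | Classical bounds (look, end) | Error with 2.78, then 1.96 | Final value needed with 2.78 | Fixed-sample power |
|---|---|---|---|---|---|---|
| 98 (planned) | 49 | 0.561 | 2.65, 1.986 | 5.17% | 1.975 | 90.4% |
| 110 (implied by halfway) | 55 | 0.500 | 2.80, 1.977 | 5.21% | 1.979 | 93.4% |
| 130 (if all consented were randomised) | 65 | 0.423 | 3.03, 1.969 | 5.26% | 1.983 | 96.5% |

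Only the first row is a target that the protocol states. The fraction 0.500 also applies to a look at patient 49 of 98, so the same bounds and error hold there.

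**6. Power after correction.** At N = 98 the noncentrality is 0.5/(0.75√(2/49)) = 3.30. For the final test alone, normal-approximation power is Φ(3.30 − 1.960) = 91.0%. It becomes Φ(3.30 − 1.975) = 90.7% or Φ(3.30 − 1.977) = 90.7%, a loss of about 0.3 percentage points.

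**The case against.** The strongest reply is that the design is settled. Every passage that states a sample size says 98, the power table supports it, and 10.1 is a consent count, not a sample size. Section 12.2 allows withdrawal between consent and induction, and section 16.3 leaves out withdrawn participants, so a consent number above 98 is reasonable. The 123 is worded as an estimate, not a cap. The error rate hardly moves between the candidate totals.

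Most of this stands, and it rules out four stronger readings that a reader might infer:

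- *The final sample size is undefined.* It is not: 98 is stated in two sections and reproduces.
- *98 and 123 conflict.* They count different things and are linked by the stated 80% rate.
- *The trial may stop anywhere from 98 to 130.* Section 10.1 gives no stopping instruction, and 15.2 commits to enrolling 98.
- *The value 2.78 shows which total was meant.* With Lan-DeMets O'Brien-Fleming-type spending, a look at 55 of 98 gives 2.77, which seems to single out 98. But the protocol never names a spending function. The classical bound is 2.80 at 50% and 2.65 at 56%, so on that reading 2.78 is closer to a true halfway look. The number does not settle the question.

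The reply does not remove the mismatches. No passage says that 130 is a ceiling or gives a loss rate after consent, and a ceiling would not make 55 half of 98. The 100 approached contradicts the 123 in its own paragraph.

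**Conclusion.** The point holds as a minor one. The planned total of 98 is sound, but 130 consented, halfway at 55, and 100 approached do not match it. The superiority look is at 56% of the planned number, not the labelled 50%.

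The numerical effect is small. Overall two-sided error is 5.17% at N = 98, against 5.21% for a true halfway look, so the timing itself does not raise the error. The excess over 5% comes from the missing final critical value and would be present at any of these totals. Power is not at risk: it is 90.4% at 98 and higher at any larger total.

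These figures assume one look, information proportional to the number of patients, 1.96 at the end, and the plan's own difference and SD.

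**What to change.** Use one set of figures in sections 10.1, 10.2, 15.2 and 18.2:

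1. State that enrolment stops at 98 randomised patients (49 per group), with about 123 approached.
2. Correct the 130 in section 10.1, or state that it is only a ceiling covering patients consented but not randomised.
3. In section 15.2, replace 100 approached and 6.25 months with 123 and about 7.7 months, and write the inflation step as 98/0.80.
4. For the DSMB look, choose one option and state the information fraction and both critical values in sections 18.2 and 15.3:
   - look at the 49th patient, with classical O'Brien-Fleming bounds of 2.797 and then 1.977; or
   - keep patient 55, call it 56% of 98, and use 2.78 at the look and about 1.975 at the end.

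Either option brings overall error to 5%. The cost is protocol wording and about 0.3 percentage points of power at the final test. No extra patients are needed.

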11.0 Local Recruitment Methods

11.1 Recruitment Process:

Participants who will be undergoing renal transplant surgery at the University of Minnesota – Fairview East Bank. Given the uncertain nature of matching organs to potential recipients, the potential recruits will be identified through the operating room schedule the day of their surgery. The research team will ensure that it does not interrupt that pre-op workflow. The nurses will be informed of the study and ahead of time.

A research assistant or one of the investigators will discuss with the patient the goals of the study and answer any questions the participant and the participant's family may have about the study. Consent will also be obtained by the research staff. Any additional questions the research assistant is unable to answer will be answered by the investigators of this study. A copy of the consent will be given to the patient, one will remain in the patient's medical record and the original will be securely stored by research staff.

11.2 Identification of Potential Participants:

Participants who will be undergoing renal transplant surgery at the University of Minnesota – Fairview East Bank. Potential participants will be approached prior to their surgery by the operating room schedule that day (see above mentioned safeguard in 11.1).

11.3 Recruitment Materials: N/A

11.4 Payment: None

12.0 Withdrawal of Participants

MEDICAL PROTOCOL (HRP-590)

PROTOCOL TITLE: Comparison of normothermia maintenance between resistive blanket and forced air warming systems in renal transplant surgery

VERSION DATE: V43 January June 6, 2022

12.1 Withdrawal Circumstances:

The patient's physicians (either surgeon or anesthesiology) may withdraw patients from the study without their consent if there are any concerns for patient safety (whether related to the study or not).

12.2 Withdrawal Procedures:

Participants may withdraw at any time from the study after consenting for participation up to induction of anesthesia and may withdraw from the study after the surgery (the participant will be unconscious after induction of anesthesia and will be unable to withdraw while under anesthesia). Data collected for the study may be retained unless the participant requests otherwise, in which it will then be deleted/destroyed. However, all typical data recorded for the intraoperative anesthetic record will continue to be collected in the patient's chart for patient care and documentation.

12.3 Termination Procedures:

The patient's physicians (either surgeon or anesthesiology) may terminate the study at any time if there are concerns for patient safety (whether related to the study or not).

13.0 Risks to Participants

13.1 Foreseeable Risks:

None beyond those routinely associated with transplant surgery and anesthesia and temperature management. Thermal injury to the skin (with or without actual burns) is listed as a risk for all warming systems that contact the skin (including both forced air and resistive blankets) but such events are exceedingly rare when the equipment is used as intended. We will use the devices according to the manufacturer's recommendations of operating the devices.

Participation in research may involve a loss of privacy due to the nature of the questions that are asked and/or data collected. However, records will be handled as confidentially as possible. No identifying information will be used in any report or publications that may result from this study. All study records will be kept in a UMN box and REDCap which are secure databases. Paper records will be kept in locked cabinets in locked rooms only accessible to study staff.

13.2 Reproduction Risks: None

13.3 Risks to Others: N/A

14.0 Potential Benefits to Participants

14.1 Potential Benefits:

MEDICAL PROTOCOL (HRP-590)

PROTOCOL TITLE: Comparison of normothermia maintenance between resistive blanket and forced air warming systems in renal transplant surgery

VERSION DATE: V43 January June 6, 2022

Aside from stated benefits from maintaining normothermia in the perioperative period in this proposal, there are no other additional benefits for subjects in participating in this study.

15.0 Statistical Considerations

15.1 Data Analysis Plan:

1. Our primary outcome variable is the patient's temperature at the end of surgery.

2. Secondary outcome variables also include:

- AUC of time versus temperature curves;
- temperatures at set points during operative period;
- blood loss volumes

All continuous measures will be summarized with mean (standard deviation) or median (interquartile range) based upon evaluation of normality using statistical tests (e.g., Shapiro-Wilk) and graphical representation (e.g., histograms, boxplots). Categorical measures will be summarized by count (percent).

The secondary outcomes are continuous measures and will be compared using two-sided two-sample t-tests for unadjusted comparisons of the groups. Adjusted comparisons will use linear regression models to account for potential confounders that may affect the outcome based upon the clinical literature.

Safety outcomes of interest include the incidence of hyperthermia, rescue warming, and incidence of thermal injury. These are categorical variables and will be compared using the χ^2 test or Fischer's exact test for unadjusted comparisons and with logistic regression models to account for potential confounders.

Final data set will be assessed for missing data, depending on rate of missing data, we will use statistical methods to account for missing data

15.2 Power Analysis:

A mean difference of 0.5°C in patient temperatures between the two devices would be clinically meaningful. However, limited data exists, so a range of standard deviations were explored to examine the different sample sizes needed at 80% and 90% power (assuming a two-sided two-sample t-test with $\alpha=0.05$).

Power	SD	N per Group	Overall N
0.8	0.25	6	12

MEDICAL PROTOCOL (HRP-590)

PROTOCOL TITLE: Comparison of normothermia maintenance between resistive blanket and forced air warming systems in renal transplant surgery

VERSION DATE: V43 January June 6, 2022

	0.5	17	34
	0.75	37	74
	1	64	128
0.9	0.25	7	14
	0.5	23	46
	0.75	49	98
	1	86	172

We will take a conservative approach by enrolling 49 patients per group (98 patients total). As this is a minimal risk study, we expect to an 80% enrollment rate; we will approach (98 + 20% = 123 patients). In 2019, the University of Minnesota Medical Canter performed approximately 240 renal transplants for a total of ~200 eligible patients or ~16 eligible patients/month; 100 total patients approached/16 eligible patients per month = 6.25 months.

15.3 Statistical Analysis:

Data will be collected in REDCap and stored in an excel spreadsheet format in box and analyzed in-house with a statistician.

All analyses will be conducted using R or SAS statistical software. Values of $p < 0.05$ will be considered statistically significant. The analyses will use the intention-to-treat approach. The primary outcome will assume a complete case analysis, but when data is missing, methods for imputation will be explored based on the amount and type of missing data, potentially including multiple imputation using the mice package in R or linear interpolation methods for measures repeated over time that are missing for sensitivity analyses.

15.4 Data Integrity:

Data will be recorded automatically into the EPIC electronic health record system and will be extracted using computer algorithms/programs that have been tested for data extraction either by the research team or by the EPIC data team at Fairview. Any data extracted from the Vigilance II monitor with the VitalDB software package will be performed in real-time to a hospital-owned computer dedicated to the research team.

Data will be stored on hospital, password-protected computers via UMN Box. This will include laptops. Data will not be stored on personal computers of any kind,

MEDICAL PROTOCOL (HRP-590)

PROTOCOL TITLE: Comparison of normothermia maintenance between resistive blanket and forced air warming systems in renal transplant surgery

VERSION DATE: V43 January June 6, 2022

including smartphones. The computers will be stored in a locked office in the hospital, and only the research team will have access to these computers.

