4.3 Biosafety: N/A

4.4 Stem Cells: N/A

4.5 Fetal Tissue: N/A

5.0 Procedures Involved

5.1 Study Design:

Single institution, prospective, randomized, unblinded superiority study of renal transplant surgery participants, with no history of previous transplant, comparing a resistive blanket warming system (Hotdog (U102); Augustine Surgical, Inc., Eden Prairie, MN, USA) to a forced air warming system (Bair Hugger, Model 635; 3M Medical, St. Paul, MN, USA).

A randomization schedule will be developed using permuted block randomization with blocks of size 2, 4, 6, and 8 assuming 1:1 allocation within each block. Data will be analyzed using an intention-to-treat protocol.

5.2 Study Procedures:

The study will involve two arms: a resistive blanket warming system arm and a forced air warming system arm. Both devices will be set to warm the patient at each device's maximum setting at the beginning and throughout the case. The hotdog's maximum setting is 39C and the Bair Hugger's maximum setting is 41C.

The patient will be randomized to either the FAWS or RBWS before arrival to the operating room. Depending on which arm they have randomized to, the

MEDICAL PROTOCOL (HRP-590)

PROTOCOL TITLE: Comparison of normothermia maintenance between resistive blanket and forced air warming systems in renal transplant surgery

VERSION DATE: V43 January June 6, 2022

participant will be placed on either the underbody FAWS or the RBWS. An upper body FAWS will be placed on top of the patient prior to incision but is only to be utilized if normothermia cannot be achieved during the surgery with either device. The warming system that the patient is randomized to will be set up on the table before the participant is brought to the OR and transferred to the operating room table. The main warming device will be turned on once the patient is positioned on the operating table. The CRNA's will be involved in the placement of the blankets. Surgeons, OR Nurse Managers, and CRNA's will be informed by research team regarding patient's involvement in the study.

After the needed standard monitors for surgery have been placed, general anesthesia will be induced and maintained with patient's hemodynamics and other vitals maintained per standard care (no additional measurements beyond standard of care which is recorded in EPIC). Standard anesthetic care of the participant will occur for the duration of the surgery.

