Patient core temperature will be measured with a nasopharyngeal temperature probe. The patient's temperature will be monitored and recorded for the duration of surgery with the selected warming system. Vital signs, including continuous blood pressure, heart rate, oxygen saturation, and end-tidal carbon dioxide, will be monitored and recorded in Epic as is routine with all anesthetics performed. Our primary outcome variable is the NP temperature as recorded at the end of the surgery.

After the surgery, the patient will be transported to the PACU in a timely fashion. Temperature measurement in the PACU will be standardized with skin temperature probes (3M Spot-On) that will be placed on the forehead prior to leaving the operating room. If there is an unexpected delay in transporting the patient to the PACU, that will be documented and the temperature upon arrival to PACU will not be valid.

Data to be collected about participants and the source records that will be used to collect those data:

From Epic:

- Age
- Sex
- MRN
- Height
- Weight
- BMI
- Date of procedure
- Procedure performed

MEDICAL PROTOCOL (HRP-590)

PROTOCOL TITLE: Comparison of normothermia maintenance between resistive blanket and forced air warming systems in renal transplant surgery

VERSION DATE: V43 January June 6, 2022

- Nasopharyngeal temperature throughout surgery (every minute)
- Time at warming system being switched (resistive blanket or forced air)
- Time when patient reaches 37°C
- Time at OR departure
- Time sign-out from PACU prior to transfer to regular nursing floor
- Blood product volume administered to patient (red blood cells, fresh frozen plasma, platelets, and cryoprecipitate)
- Recorded incidence of rescue warming used for when patient's temperature is at 35.5°C (requiring rescue means the need to turn on the additional forced air warming device that may be due to severe hypothermia and uncontrolled bleeding)

Individually Identifiable Health Information: See above

HIPAA Agreement: Attached

5.3 Study Duration:

Individual Subject Participation Duration: Patients will be in the study for their scheduled procedure and for 1 hour following their procedure. Duration of the surgical procedure, is typically 2-5 hours depending on the surgery required. Following the study, participants will not be approached at any time, for any reason as it pertains to their study participation.

Total Study Duration (all Participants): approximately 1 year

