7.2 Sharing of genetic testing: N/A

8.0 Study Population

MEDICAL PROTOCOL (HRP-590)

PROTOCOL TITLE: Comparison of normothermia maintenance between resistive blanket and forced air warming systems in renal transplant surgery

VERSION DATE: V43 January June 6, 2022

8.1 Inclusion Criteria:

- Eighteen (18) years to 90 years old
- Undergoing elective renal transplantation

8.2 Exclusion Criteria:

- Previous surgery involving organ transplantation or nephrectomy. These patients are at higher risk of blood loss, making temperature regulation subject to more variables outside our control.
- ~~End stage renal disease with decreased or no urine output from normal.~~
- Previous upper extremity amputations
- Ongoing sepsis or other infection
- Thyroid dysfunction
- Emergency surgery
- Refusal of consent to participate in study
- Pregnancy

8.3 Screening:

First, potential participant's chart in Epic will be accessed to ensure they are not "Research Opt Out" (will not be approached by research team). Participants will be seen in the preoperative holding area before surgery. Participants will be identified before the procedure either by participating anesthesiologists or transplant surgeons when an organ is available and a renal transplant surgery is scheduled. An approved member of the research team will be notified when the case is scheduled and the recipient has been sent for. This individual will then discuss the nature of the study and obtain consent. In all cases, a member of the anesthesia team will be available (either in person or via phone) to directly answer any questions that cannot be addressed by a non-physician member of the team.

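### A cheap improvement, not an error: adjust the comparison of end-of-surgery temperature for one pre-warming chart temperature, and take the interim Z from the same model

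*Combined protocol and SAP*

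**What the plan says.** - **Outcome.** Section 5.2: "Our primary outcome variable is the NP temperature as recorded at the end of the surgery". Section 15.1 repeats the outcome and attaches no method to it.
- **Named methods.** Section 15.1: "The secondary outcomes are continuous measures and will be compared using two-sided two-sample t-tests". The adjusted linear regressions, with covariates left open, are in the same paragraph.
- **Sizing.** Section 15.2 sizes the trial for a 0.5 °C difference at two-sided alpha 0.05, "assuming a two-sided two-sample t-test". It takes 49 per group from the row for 90% power and SD 0.75.
- **Rules for the primary outcome.** Section 15.3 gives intention-to-treat, p < 0.05 and "The primary outcome will assume a complete case analysis". It gives no model.
- **Interim look.** Section 18.2 stops the study for superiority at the 55th patient, "based on an intergroup Z-score difference of 2.78". It does not say which estimate supplies the Z.
- **Temperatures collected.** The list in 5.2 has NP temperature every minute during surgery and none from before warming. On timing, 5.2 says "The main warming device will be turned on once the patient is positioned on the operating table" and then "After the needed standard monitors for surgery have been placed, general anesthesia will be induced".
- **A starting value elsewhere.** The abbreviations list defines the AUC, a secondary outcome, as change from T_i, without saying when T_i is taken.

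**The concern.** End-of-surgery temperature is likely to depend in part on the temperature at which the patient arrived. A comparison that ignores the starting value leaves that share of the variance in the error term, and it leaves any chance difference between arms in starting temperature uncorrected. The usual remedy, one baseline covariate in a linear model, costs little if the value is already charted.

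The plan also has adjusted and unadjusted methods side by side in 15.1 without saying which applies to the primary outcome. The trial is unblinded (5.1) and has a stopping rule. The choice should therefore be settled before outcomes are compared by arm, and settled the same way for the interim Z.

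**Working it through.** **Inputs from the documents.** Difference 0.5 °C, SD 0.75 and two-sided alpha 0.05 (10.2, 15.2); 49 per group (15.2); 1:1 allocation (5.1); interim look at 55 patients with threshold 2.78 (18.2).

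**Assumed.** Rho, the correlation between a pre-warming chart temperature and the final NP temperature, from 0 to 0.5. A low value is plausible. The chart reading may come from another body site, surgery lasts 2 to 5 hours (5.3), and section 8.2 excludes "Ongoing sepsis or other infection" and thyroid dysfunction, which narrows the spread at the start. Rescue warming at 35.5 °C (4.2) raises the lowest outcomes and may weaken rho further.

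**Step 1: the plan's own figure.** The noncentral t calculation gives 48.26 per group for 90% power at SD 0.75, rounded up to 49. All eight rows of the 15.2 table reproduce. At 49 per group the standard error is 0.75 × √(2/49) = 0.1515, the noncentrality is 0.5/0.1515 = 3.30, df = 96, and power is 90.4%.

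**Step 2: add one covariate.** Residual SD = 0.75 × √(1 − rho²) and df = 95. For power, the standard error is multiplied by √(95/94) = 1.0053 to allow for chance imbalance in the covariate.

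| Analysis | Residual SD | Power | 95% CI half-width (°C) |
|---|---|---|---|
| t-test | 0.750 | 90.4% | 0.301 |
| rho 0 | 0.750 | 90.1% | 0.301 |
| rho 0.1 | 0.746 | 90.4% | 0.299 |
| rho 0.2 | 0.735 | 91.2% | 0.295 |
| rho 0.3 | 0.715 | 92.6% | 0.287 |
| rho 0.5 | 0.650 | 96.3% | 0.261 |

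The half-widths leave out the 1.0053 factor, which would add less than 0.002 °C. Break-even is near rho 0.1. At rho 0 the covariate costs 90.4 − 90.1 = 0.3 points.

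If the true SD is 1.0, the t-test has 68.8% power. The model has 68.3% at rho 0, and 70.1%, 72.4% and 80.3% at rho 0.2, 0.3 and 0.5.

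**Step 3: patients without the covariate.** Suppose 10% lack it (an assumption). Dropping them gives power of 88.5%, 90.1% and 94.7% at rho 0.2, 0.3 and 0.5. Imputing the overall mean, with residual variance 0.75² × (1 − 0.9 × rho²), gives 91.4%, 92.6% and 96.0%. Neither set includes the imbalance factor. Dropping patients would cancel the gain at rho 0.2 and 0.3.

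**Step 4: the interim look.** Take 27 against 28 patients. The expected unadjusted Z at a true 0.5 °C is 0.5 / (0.75 × √(1/27 + 1/28)) = 2.47. Dividing by √(1 − rho²) gives 2.52, 2.59 and 2.85 at rho 0.2, 0.3 and 0.5. The simulated share of trials in which the two analyses disagree on crossing 2.78 is:

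| True difference | rho 0.2 | rho 0.3 | rho 0.5 |
|---|---|---|---|
| 0.5 °C | about 7% | about 10% | about 20% |
| 0.25 °C | about 2% | about 3% | about 7% |
| none | 0.4% | 0.6% | 0.9% |

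**Step 5: the price of an open choice.** With no true difference and 49 per group, claiming success if either analysis has p < 0.05 gives a simulated type I error of about 6.0%, 6.4% and 7.3% at rho 0.2, 0.3 and 0.5.

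**The case against.** The strongest reply is that the t-test is the natural default. The trial is sized on it, and 15.1 puts unadjusted t-tests first for continuous outcomes. One sentence naming it would close any open choice, and with it the type I figures in step 5. That stands: those figures are a reason to name one model in advance, not a reason for the covariate.

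It also stands that rho is unknown, that the documents do not say a pre-warming temperature is routinely charted, and that rescue warming could push rho towards the region of no gain. An availability check adds a decision during an open trial. That is harmless only if it is made without reference to arm and before any comparison by arm.

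The plan does not ignore starting temperature altogether, since the AUC definition uses T_i. That concerns a secondary outcome, its timing is undefined, and nothing carries it into the primary comparison.

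Three stronger readings are tempting, and the documents support none of them.
- A reader might infer that the primary analysis is invalid or the trial too small. The unadjusted t-test is valid under randomisation, and the sample size reproduces exactly.
- A reader might infer that up to one trial in five would stop differently under the two analyses. That holds only if the true difference is 0.5 °C and rho is 0.5. With no difference it is under 1%.
- A reader might infer an inflated type I error. Nothing in the plan says that the better of two results will be reported.

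**Conclusion.** This is a worthwhile improvement at low cost and not an error. The implied t-test is sound. Adjusting for one pre-warming temperature is as good or better once rho exceeds about 0.1. Against 90.4% for the t-test, the gain is about 0.8 points at rho 0.2, 2.2 at 0.3 and 5.9 at 0.5, with a loss of about 0.3 at rho 0. The possible gain is larger if the SD is nearer 1.0, which matters because 15.2 itself says that data on the SD are limited.

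The size rests wholly on an assumed rho. The power figures also ignore the interim look, as 15.2 does. Whichever model is chosen, the final analysis and the interim Z should come from the same one. No change to the sample size is needed.

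**What to change.** 1. In 15.1, state the primary analysis as a linear model of end-of-surgery NP temperature on randomised arm plus one covariate: the last routine chart temperature before the main warming device is switched on. Use no other covariate in the primary model.
2. Fix the time window and measurement site for that value, and add it to the data list in 5.2. Do not substitute the first NP reading. On the sequence in 5.2 it probably follows the start of warming, so it could absorb part of a device effect.
3. If the covariate is missing, impute its overall mean, ignoring arm, so that the complete-case rule in 15.3 applies to the outcome only.
4. In 18.2, take the interim Z from the same model.
5. Check availability without reference to arm, and fix the choice before any comparison by arm, including the interim look.
6. Report the unadjusted t-test as a sensitivity analysis. If no pre-warming value is routinely charted, name the t-test as the primary analysis and for the interim look.

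The cost is a few sentences in 15.1 and 18.2, one chart field and one availability check. The downside is a gain that may be nil, or a loss of about 0.3 power points if rho is 0.
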